Specific Aim 1: To investigate that increased DA transmission normalizes reward responsiveness and optimism in females with histories of CSA. We will use reward paradigms from our pilot work in conjunction with a pharmacological challenge to test that decreased phasic DA transmission within mesolimbic regions plays a key role in CSA sequelae. We hypothesize that increased phasic DA release – achieved through presynaptic DA autoreceptor blocking by means of single low dose of the D₂/D₃ antagonist amisulpride – will improve positive reinforcement learning and boost activation in reward-related brain regions, particularly the ventral and dorsal striatum (**Hypothesis 1a**). Due to hypothesized downregulation of mesolimbic DA pathways, we expect that individuals with CSA and current MDD (“CSA/MDD”) will show the largest improvements. Confirming that a well-functioning reward system is a marker of resilience, adults with CSA without lifetime psychopathology (“CSA/RES”) will show normative activation and performance under placebo (**Hypothesis 1b**). We also hypothesize that increased phasic DA release – achieved through amisulpride – will re-orient MDD individuals from a pessimistic outlook to an optimistic outlook as measured by the Optimism Bias Task (**Hypothesis 1c**). In addition, under placebo, MDD participants will show a pessimistic outlook as compared with healthy controls (**Hypothesis 1d**).

Specific Aim 2: To investigate dopamine transporter and its relation to reward processing in females with CSA history. We will utilize positron emission tomography (PET) and a highly selective radioactive ligand (¹¹C-altropane) to assess DAT binding in CSA adults. Animal studies have shown that early adversity leads to DAT downregulation within mesolimbic regions. In humans, we have observed links between altropane binding and depressive symptoms, the most common CSA sequelae). Based on our data, we expect that, relative to control and CSA/RES subjects, CSA/MDD adults will show reduced altropane binding (**Hypothesis 2a**). We further hypothesize that, among the CSA/MDD group, reduced DAT will correlate with blunted reinforcement learning and striatal activation (**Hypothesis 2b**).

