Saliva samples will be acquired for cortisol assessment 20 min after arrival (baseline saliva sample), immediately following the stress manipulation (acute saliva sample), following block 1 of the second PRT (post-stressor saliva sample #1), following block 2 of the second PRT (post-stressor saliva sample #2), and 68 minutes following the stress manipulation (recovery saliva sample). Saliva samples will be collected using passive-drooling cryovials (Salimetrics, State College, PA, USA). Subjects will be instructed to not eat, drink, smoke, brush their teeth or engage in physical activity for at least 30 min before the session. To avoid contamination from food particles, water will be handed to rinse oral cavities prior to data collection. In our prior work, intra- and inter-assay coefficients of variance were <10% (Koslov et al 2011). The protocol is in line with large cortisol studies (e.g., Lederbogen et al 2010) and adheres to the policies on tissue storage and transfer of McLean Hospital.

fMRI Session

This session will take place at the McLean Hospital Imaging Center. Participants will complete the Monetary Incentive Delay (MID) task during fMRI (collected using the 3T MR scanner). Because the pharmacokinetics of amisulpride are linear and a first peak plasma concentration is seen 1-1.5 hr after oral administration (Curran & Perry 2001), fMRI scanning will start 1 hr after administration of amisulpride (or placebo). The dose (50 mg) was selected based on prior studies (e.g., Hamon-Vilcot et al 1998; Samuels et al 2006), and the observation that all prior studies in depressive disorders have used 50 mg/day doses. Using a double-blind design, half of the participants in each group will be administered amisulpride (or placebo).

Amisulpride is a substituted benzamide neuroleptic with high affinity for D₂/D₃ DA receptors and low affinity for other receptors, and higher binding to DA receptors in limbic (e.g., NAc) than nigrostriatal regions. Animal studies have shown that at low doses, amisulpride preferentially blocks presynaptic DA autoreceptors, leading to increased DA synthesis and release and prohedonic effects (Coukell et al 1996; Schoemaker et al 1997).

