Subjects will be paid \$15/hour for the SCID session (session 1), up to \$70 for the ERP session including \$38 for completing the EEG and up to \$32 on the probabilistic reward task, up to \$150 for the fMRI session including \$100 for completing the session and up to \$50 on the MID task, and \$200 for the PET session. In addition, participants who complete all four sessions of the study will earn an additional \$75. Lastly, if participants complete only part of a study session, they will be compensated in a prorated manner, such that if they complete half of a study session, they will be compensated half of the total amount (e.g., participant completes half of the PET scan session, he/she will be compensated \$100). If the participant completes all of the sessions, they can earn up to \$555. The subset of subjects who participate in the additional skin fibroblast study (n=20) will be compensated \$100.

Randomization

For protocol 2010-P-002593, all subjects in study are administered a single low dose of amisulpride (50 mg) in order to test the role of dopaminergic mechanisms in the pathophysiology of MDD. This proof-of-mechanism study uses a double-blind, placebo-controlled between-subject design (for each group in study, 50% of the subjects in each group will receive placebo, with the remaining 50% receiving a single dose of amisulpride), involves a single MRI session, and does not include a treatment component. Though data collection has not yet been completed, the blind was broken as of May 2016 to conduct preliminary analyses. Accordingly, the medication blind will be broken as of November, 2016 in order to allow further analyses. In order to preserve the scientific integrity of the study, we propose the following precaution:

The Research Assistant responsible for running participants ([name]), the study doctors ([name], [name]), and any other member of the [name] Lab who directly interacts with participants will remain blind to drug group assignment. Accordingly, if we discover during statistical analyses that a few participants yielded unusable data (e.g., due to excessive motion artifacts), we will be able to enroll and test a few final participants in a fully unbiased way.

b. Drugs to be used

Amisulpride

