Procedure: Because the pharmacokinetics of amisulpride are linear and similar across gender, and a first peak plasma concentration is seen 1-1.5 hr after oral administration (Ascalone et al, 1996), fMRI scanning will start 1 hr after administration of amisulpride (or placebo). During the one-hour wait between the administration of amisulpride (or placebo), participants may read or view a neutral film. During this time, experimenters will carefully monitor participants to assess the presence/absence of side effects. A designated study physician will be present at the neuroimaging facility throughout the session with a response time of 2-3 minutes in case study participants experience adverse side effects during the fMRI scanning. After one hour, participants will be asked to enter the scanner, and data collection will begin. The dose (50 mg) was selected based on prior studies (Hamon-Vilcot et al., 1998; Samuels et al, 2006), and the observation that all prior studies using amisulpride in depressive disorders have used 50 mg/day doses (see above). Using a double-blind design, half of the participants in each group will be administered amisulpride, whereas the other half will receive placebo.

c. Devices to be used

Not applicable

d. Surgical interventions

Not applicable

e. Data to be collected

Please see below for details on data collected and analyses performed.

VI. BIostatistical Analysis

a. Specific data variables being collected

Probabilistic Reward Task (PRT)

The main variable is response bias, which assesses participants' preference for the stimulus paired with more frequent reward, and will be calculated using a published formula ([name] et al 2005). To test the specificity of findings, control analyses will be run on discriminability, which provides a measure of the ability to discriminate the two stimuli. To test **Hypothesis 3a** and **3b**, *Group* (CSA/MDD, CSA/RES, MDD, controls) x *Block* (1,2,3) ANOVAs will be run for response bias and discriminability.

Implicit Learning Serial Reaction Time Task (SRTT)

SRTT data will be analyzed using established procedures (median reaction times for blocks presenting random vs. the predetermined sequence will be calculated; (Kathmann et al, 2005). If group differences emerge in procedural learning, SRTT data will be used as covariates/regressors in all analyses.

Optimism Bias Task

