Analyses will be conducted using FreeSurfer (Fischl et al 2002, 2004). Volumetric analysis will be conducted and, if applicable, fMRI data will be adjusted for volumetric group differences. Pre-processing will include motion/slice-time correction, removal of slow linear trends, intensity normalization, and spatial smoothing (6-mm). The hemodynamic response will be modeled as a gamma function (2.5 s delay to rise, 1.25 s dispersion time) and convolved with stimulus onsets. Data will be analyzed using two approaches: an ROI approach to evaluate *a priori* hypotheses and a whole-brain approach to test finding specificity. In the first, regression coefficients (“beta weights”) will be extracted from ROIs obtained from FreeSurfer’s parcellation and selected based on prior studies (Knutson & Cooper 2005). ROIs will include basal ganglia regions (globus pallidus, NAc, caudate, putamen), dorsal/ rostral anterior cingulate, vmPFC, and OFC. For each subject and ROI, beta weights will be entered into *Group* x *Condition* (amisulpride, placebo) x *Hemisphere* x *Trial* (reward, loss, no-incentive) ANOVAs. We expect that the main effects of *Group* (controls \approx CSA/RES > MDD > CSA/MDD) and *Condition* (amisulpride > placebo) will be significant. Moreover, although amisulpride will increase basal ganglia responses to reward – but not punishment or no-incentive – cues in all groups, we expect that the CSA/MDD group will show the greatest improvements (significant *Group* x *Condition* x *Cue* interaction). Planned contrast will show no difference between controls and CSA/RES receiving placebo, and CSA/MDD subjects receiving amisulpride will show similar activation as controls under placebo. In the second approach, whole-brain analyses will be run. Each subject’s data will first be re-sampled into Talairach space and random effects analyses will be run. Significance levels in the fMRI data will be set to yield a corrected mapwise significance level of $p < .05$.

PET Analyses

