Images will be acquired in 3-D mode and reconstructed using a filtered back projection method while modeling the point spread function of the HR+ in the projector to ensure recovery of in-plane spatial resolution of ~ 4.5 mm without increasing noise levels. All projection data will be corrected for nonuniformity of detector response, dead time, random coincidences, and scattered radiation. After realignment, motion-corrected PET frames will be summed, registered to the respective MRI (Woods et al 1993), and transformed into stereotaxic space (Talairach & Tournoux 1988) based on an automated feature-matching algorithm (Collins et al 1994). ROIs will be manually drawn on high-resolution MRI images for dorsal (caudate, putamen) and ventral (NAc) striatal regions. The cerebellum will be used as reference tissue. A simplified reference tissue method (Gunn et al 2001; Lammertsma & Hume 1996) will be used to calculate binding potential. To increase statistical power, a Bayesian method recently developed by the MGH team will be used (Alpert et al 2009; Fang et al 2010). Briefly, this method utilizes prior normative data in a cohort of 51 healthy subjects who underwent 60-min ^{11}C -altropane scan. Bayesian estimates yielded a substantial variance reduction in SRTM parameters, making it possible to reduce the sample size needed to achieve a given power level by $\sqrt{2}$. ANOVAs contrasting age-adjusted altropane binding (covariates: smoking & phase of menstrual cycle) across the groups will be performed. Correlational analyses between binding and (1) response bias in the probabilistic reward task, and (2) beta weights in striatal regions during the reward task, will be run.

Skin Fibroblast Analyses

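### The planned Hypothesis 2b correlation of DAT binding with striatal beta weights names no drug term, although half of the CSA/MDD scans are taken on amisulpride

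*Combined protocol and SAP*

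**What the plan says.** Hypothesis 2b (section II, Specific Aim 2) predicts that, within the CSA/MDD group, "reduced DAT will correlate with blunted reinforcement learning and striatal activation". The matching analysis is one sentence at the end of section VI.a, PET Analyses: binding will be correlated with PRT response bias, "and (2) beta weights in striatal regions during the reward task, will be run". It names no drug term, stratification or restriction to placebo.

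The MID is the only reward task performed in the scanner. The study "involves a single MRI session, and does not include a treatment component" (section V.a, Randomization). Scanning starts one hour after dosing (section V.a, fMRI Session), and "half of the participants in each group will be administered amisulpride, whereas the other half will receive placebo" (section V.b).

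Elsewhere the plan is explicit about such terms:

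- Section VI.a, fMRI Analyses, makes drug condition a factor in the ANOVAs of the same beta weights. It expects amisulpride to raise basal ganglia responses to reward cues and adds that "we expect that the CSA/MDD group will show the greatest improvements".
- The sentence just before the correlation names covariates for the group comparison: "ANOVAs contrasting age-adjusted altropane binding (covariates: smoking & phase of menstrual cycle) across the groups will be performed".
- Hypothesis 1b states a placebo restriction where one is meant: CSA/RES participants "will show normative activation and performance under placebo".

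Section VI.c only refers back to the text above it. The one covariate rule that reaches all analyses concerns the SRTT.

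**The concern.** About half of the CSA/MDD beta weights are measured under a drug that the plan expects to shift them. An analyst who follows the sentence literally would compute one unadjusted correlation across both arms. Because the drug is randomised, it is unrelated to binding in expectation. It therefore does not create a false association; it adds variance to the beta weights, which pulls the correlation towards zero and lowers power, in the group where the plan expects the largest drug effect.

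If amisulpride also changes the slope of activation on binding, one pooled coefficient describes neither arm.

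An analyst who instead adjusted, or restricted to placebo, would be making an unplanned choice. That matters more here because section V.a (Randomization) reports that the blind was broken in May 2016 for preliminary analyses, before data collection had ended.

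**Working it through.** **Plan's own figure.** None exists for Hypothesis 2b. Section VI.d covers group and drug differences only and gives no expected correlation.

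**Inputs from the documents.** There are 23 participants per group (section IV.a), allocated 1:1 to drug and placebo. I take 11 amisulpride and 12 placebo. The first sentence under Randomization says that all subjects receive amisulpride, whereas the next sentence and sections V.a (fMRI Session) and V.b give a half-and-half split; these passages should be reconciled. Alpha is 0.05, taken as two-sided.

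**Assumptions.** The within-arm correlation r is 0.3 or 0.5. The drug shift d, in within-arm SD units, runs from 0 to 1.80. Slopes are equal in the two arms. Two values of d are borrowed from section VI.d to mark the upper end:

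- 1.80 is the bupropion effect, (1.88 + 1.64 + 1.89)/3, in regions that are not the striatal ROIs of the PET section.
- 1.15 is the plan's mean fMRI effect, (0.78 + 0.87 + 1.80)/3, which mixes two case-control effects and one drug effect.

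**Attenuation.** With a share p on drug, independent of binding, the variance of the beta weight rises from 1 to 1 + p(1−p)d², while its covariance with binding is unchanged. Hence

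pooled r = r / sqrt(1 + p(1−p)d²), with p(1−p) = (11 × 12)/23² = 0.2495, close to 1/4.

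At d = 1.15: 1/sqrt(1 + 0.2495 × 1.3225) = 0.867, so r = 0.5 becomes 0.434.

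**Power by Fisher z at r = 0.5, d = 1.15.**

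- No drug term: atanh(0.434) × sqrt(23 − 3) = 0.464 × 4.472 = 2.08; Φ(2.08 − 1.96) ≈ 0.55.
- Drug partialled out: atanh(0.5) × sqrt(23 − 4) = 0.549 × 4.359 = 2.39; Φ(2.39 − 1.96) ≈ 0.67.

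**Simulation** (60,000 replicates per cell, 11/12 split):

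| r | d | Attenuation | Power, no drug term | Power, drug term |
|---|---|---|---|---|
| 0.5 | 0 | 1.00 | 0.707 | 0.687 |
| 0.5 | 0.3 | 0.99 | 0.697 | 0.688 |
| 0.5 | 0.5 | 0.97 | 0.676 | 0.690 |
| 0.5 | 0.8 | 0.93 | 0.627 | 0.688 |
| 0.5 | 1.15 | 0.87 | 0.556 | 0.689 |
| 0.5 | 1.80 | 0.74 | 0.413 | 0.687 |
| 0.3 | 0.5 | 0.97 | 0.275 | 0.279 |
| 0.3 | 0.8 | 0.93 | 0.252 | 0.279 |
| 0.3 | 1.15 | 0.87 | 0.223 | 0.279 |
| 0.3 | 1.80 | 0.74 | 0.173 | 0.279 |

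Type I error without the drug term is 0.049 at d = 1.15 and 0.050 at d = 1.80.

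**Sample-size equivalent at d = 1.15.** The squared ratio of Fisher z values is (0.549/0.464)² = 1.40 at r = 0.5, and 1.35 at r = 0.3.

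**Which d fits the plan's expectations?** Section VI.a (fMRI Analyses) expects CSA/MDD participants on amisulpride to resemble controls on placebo. The drug effect would then equal the case-control deficit, for which section VI.d prints means of 0.78 and 0.87. At r = 0.5 these give 0.63 vs 0.69 and 0.62 vs 0.69.

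**Unequal slopes at d = 1.15.**

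| Correlation, placebo / amisulpride | No drug term | Drug term | Placebo only | Interaction test |
|---|---|---|---|---|
| 0.5 / 0 | 0.19 | 0.23 | 0.40 | 0.20 |
| 0.5 / 0.25 | 0.34 | 0.43 | 0.40 | 0.09 |

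**The case against.** The sentence is an outline. It names no coefficient, group, trial type or covariate, and a partial correlation would fit its wording; drug is already a factor for the same beta weights in the fMRI section. On that view, drug handling is unspecified rather than wrong. This stands in part. But the plan states its drug factors, covariates and placebo restrictions where it intends them, so the pooled, unadjusted reading is the plainer one. Under either reading the text needs the same added sentence.

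The size rests on assumed values. This stands. At d = 0.3 the drug term slightly lowers power, and at d = 0.5 it adds about one point. The larger losses need d of about 0.8 or more.

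The main figures assume equal slopes. If the participants with the lowest DAT gain most from the drug, the slope flattens on amisulpride, and simple adjustment recovers little: 0.19 to 0.23 in the extreme case above. This stands, and it is why the remedy must include arm-specific slopes and a placebo-only analysis.

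Finally, 23 is a ceiling, because section IV.a requires only two completed imaging sessions, so fewer participants may have both PET and fMRI. With 18 participants (9/9, assumed), r = 0.5 and d = 1.15, power is 0.44 vs 0.56. At the r values considered, the drug term does not make Hypothesis 2b well powered; sample size is the larger limit. That bounds the benefit but does not argue for leaving avoidable variance in the analysis.

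**Conclusion.** The concern holds. The planned correlation names no drug term for an outcome measured under randomised drug, and nothing elsewhere in the documents supplies one. Read plainly, the consequence is an attenuated correlation and lost power, not a false positive. At r = 0.5 with equal slopes, the loss is about 6 power points at d = 0.8, 13 at d = 1.15 and 27 at d = 1.80, and it is negligible at d of 0.5 or less. Both r and d are assumptions. The scope is limited to the beta-weight half of Hypothesis 2b: the PRT half is untouched, because no study drug is given in the ERP session, and no main group or drug comparison is affected. This is a cheap improvement that should be made, not a defect that undermines the study.

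**What to change.** In section VI.a, PET Analyses:

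- Replace the beta-weight correlation with a regression of striatal beta weight on altropane binding plus drug arm, reported as a partial correlation. State that it is run within CSA/MDD; the PET section does not name the group.
- Report the drug-by-binding term with the slope in each arm.
- Report the placebo-only correlation as a sensitivity analysis whatever the interaction p-value, since that test has power of only about 0.20 even for slopes of 0.5 and 0.
- Leave the PRT response-bias correlation unchanged.
- Date the change, given the unblinded preliminary analyses.

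The cost is one degree of freedom (two with the interaction) and one line of analysis code. If the drug has no effect, power at r = 0.5 falls by about 2 points, from 0.707 to 0.687. No new data or visits are needed.

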
concentrations of electrolytes, BUN, SGOT, SGPT, CPK, alkaline phosphatase, total bilirubin, albumin, total protein, blood pregnancy test, TSH, eGFR, and electrocardiogram (EKG), and a urine drug test. These tests must be performed within four weeks prior to amisulpride administration.

Preliminary screening for sex, handedness, neurological disorders, exclusionary physical conditions, medication status, weight, history of childhood trauma and history of depression, and MRI and PET safety will take place at the time of the initial telephone contact or interview or via the online screening survey on RedCap (a Partners secure website). Subjects will be re-screened for MRI safety at the beginning of the fMRI session.

To avoid the confounding effects of medication, only subjects off medication will be considered. Importantly, no subject will be requested to discontinue treatment for the purpose of participating in the studies proposed here. Further, if any subject becomes emergently ill or suicidal, access to emergency clinical care will be provided according to established procedures at McLean Hospital. If at any point between signing of consent and the conclusion of the second session, a subject becomes suicidal, homicidal, manic, or psychotic, (s)he will be withdrawn from the study and appropriate care and resources will be provided. Depending on the outcome of the first session, eligible participants will be assigned to one of four groups: (1) CSA between the ages of 5-14 with current diagnosis of MDD (*CSA/MDD*), (2) CSA between the ages of 5-14 without current or past diagnosis of Axis I or II disorders (*CSA/RES*), (3) current diagnosis of MDD without a history of CSA (*MDD*), and (4) healthy controls. Each group will contain 23 subjects who complete at least two imaging sessions (n=23/group).

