A *Group* (CSA/MDD, CSA/RES, MDD, controls) x *Drug* (amisulpride, placebo) x *Trial Type* (PSST: Choose A, Avoid B or MID: Reward, loss, no-incentive) ANOVA will be run. Based on prior findings, we expect a significant *Drug x Trial Type* interaction, due to larger positive reinforcement learning but lower negative reinforcement learning in the amisulpride relative to the placebo group. Moreover, although amisulpride is expected to affect reinforcement learning in all groups, we hypothesize that CSA/MDD subjects will show the largest gains, leading to a significant *Group x Drug x Trial Type* interaction. Planned contrast will show no difference in positive reinforcement learning between controls receiving placebo and CSA/MDD subjects receiving amisulpride. To test Hypothesis 1b, a *Group x Drug x Trial* ANOVA is expected to yield no group differences between CSA/RES and controls and significant differences to the CSA/MDD in the placebo condition and CSA/MDD subjects receiving amisulpride.

fMRI Analyses

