Comparison of Molecular and Cellular Properties of Converted DA Neurons from Fibroblasts of MDD/CSA (n=8), CSA/RES (n=4), and Psychiatrically Healthy Subjects (n=8): Once we optimize conversion of fibroblasts to mDA neurons, we will use these biopsied fibroblasts to convert them to mDA neurons using our optimized protocol. To evaluate whether converted DA neurons from each group have distinct properties, we will test their ability to synthesize and release DA in response to membrane depolarization. We will treat *in vitro* differentiated cells with 50 mM KCl for 30 minutes and assess DA release by HPLC. Media will be collected after 30 min then concentrated perchloric acid (PCA) will be added to a final concentration of 0.1 M PCA/0.1mM EDTA. The DA content of the supernatants will be measured by reverse-phase HPLC. We will also compare mRNA expression patterns for dopamine-related genes such as synthesizing (TH and AADC), uptake (DAT), degrading (MAO and COMT), and storage function (VMAT2) at mRNA and protein levels in converted mDA neurons of each group.

Plasma Samples

Concentrations of pro- and anti-inflammatory cytokines and related receptors will be assessed using enzyme-linked immunosorbent assays (ELISA, R&D systems, Minneapolis, MN). All assays will be performed at the CLIA-certified Harvard Catalyst Central Laboratory (HCCL) in accordance with manufacturer specifications, and will be run in duplicate.

b. Study endpoints

Not applicable

c. Statistical methods

Please see above.

d. Power analysis

Sample size and power calculations

Sample size was estimated after considering effect sizes obtained in preliminary studies. Effect sizes were calculated using $p = 0.05$ for detecting differences between (1) controls vs. CSA/MDD, and (2) CSA/MDD receiving a DA challenge vs. placebo. Based on these estimates and allowing for 5% data loss, the sample size is 92 (23 subjects/group). In our study using the PSST task proposed, relative to controls, women with histories of CSA and MDD showed lower accuracy in trials in which they needed to rely on reward (Cohen's $d = -0.85$). In a study using the probabilistic reward task, we found that unmedicated MDD subjects had significantly reduced response bias compared to controls ($d = -0.70$; [name] et al 2009b). In another study using the same task, we found that healthy subjects receiving

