a single dose of pramipexole – hypothesized to reduce phasic DA transmission due to inhibition of presynaptic autoreceptors – had significantly lower reward learning than those receiving placebo ($d = -1.45$; [name] et al 2008b). In an fMRI study using the MID task, relative to controls, a maltreated sample showed weaker activation to reward-predicting cues in the left putamen ($d = -0.54$) and left pallidus ($d = -1.02$), yielding a mean effect size of -0.78 . In a separate study using the MID task, unmedicated MDD subjects showed weaker activation than controls in response to gains in the caudate ($d = -0.98$), left NAc ($d = -0.73$) and left putamen ($d = -0.78$) during reward anticipation ([name] et al 2009a), yielding a mean effect size of -0.87 . In a pharmacological fMRI study in unmedicated MDD subjects we found that a single 150 mg dose of Bupropion – assumed to partially block DAT – increased reward-related responses in components of the brain’s reward circuit, including the midbrain ($d = -1.88$), subcallosal gyrus ($d = -1.64$), and SLEA ($d = -1.89$), leading to an mean effect size of -1.80 ([name] et al 2008a). In sum, based on the effect sizes we have observed for the behavioral (mean $d = -1.00$) and fMRI (mean $d = -1.15$) components, a total of 92 subjects leads to a power >0.95 of detecting group differences.

For the PET study, secondary analyses of altropane data collected in ADHD and control samples (Spencer et al 2007) indicated that a history of depression and/or current subthreshold depressive symptoms were linked to decreased DAT binding ($d = -0.58$). Because this sample was carefully screened to exclude current, clinically significant depressive symptoms and because analyses did not involve the recently developed Bayesian method, we expect that effect size between control and CSA/MDD groups will be larger (expected $d > 0.80$). Thus, 92 subjects leads to a power >0.85 of detecting group differences.

VII. RISKS AND DISCOMFORTS

a. Complications of surgical and non-surgical procedures

Maastricht Acute Stress Test (MAST)

The risks associated with the stress manipulation are minimal. This manipulation has been implemented in numerous labs due to its efficiency and safety. First of all, it is a non-intrusive manipulation that causes only very minor pain, if any. Secondly, at all times participants are allowed to remove their hand from the cold water and thus immediately stop the manipulation.

EEG

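### The power figure above 0.95 does not carry over to the amisulpride v placebo contrast in CSA/MDD (11 v 12), which the plan names as a basis for its sample size: the plan's own averaged effects give 0.63 and 0.75 there

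*Combined protocol and SAP*

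**What the plan says.** Section VI.d (Power analysis) states: "Effect sizes were calculated using $p = 0.05$ for detecting differences between" two pairs, controls v CSA/MDD and "CSA/MDD receiving a DA challenge vs. placebo". It does not say whether the test is one- or two-sided. The resulting total is 92, or 23 per group, after an allowance of 5% for data loss.

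On numbers per arm, section IV.a says: "Each group will contain 23 subjects who complete at least two imaging sessions". The Randomization text in section V says that "50% of the subjects in each group will receive placebo, with the remaining 50% receiving a single dose of amisulpride".

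The effect sizes in VI.d, given here as absolute values, are of two kinds:

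- Case-control deficits: 0.85 on the PSST (women with CSA and MDD), 0.70 on the probabilistic reward task (unmedicated MDD), and for the MID task 0.78 (a maltreated sample) and 0.87 (unmedicated MDD).
- Drug effects: 1.45 for single-dose pramipexole in healthy subjects on the probabilistic reward task, a drug "hypothesized to reduce phasic DA transmission due to inhibition of presynaptic autoreceptors", and 1.80 for bupropion 150 mg in unmedicated MDD on fMRI. Neither is amisulpride.

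The section then quotes mean effects of 1.00 (behaviour) and 1.15 (fMRI) and concludes that 92 subjects give power above 0.95 for differences between groups. It gives no separate figure for the drug contrast.

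The predicted size of the drug effect appears indirectly in section VI.a. For behaviour: "Planned contrast will show no difference in positive reinforcement learning between controls receiving placebo and CSA/MDD subjects receiving amisulpride". The fMRI paragraph likewise expects CSA/MDD on amisulpride to resemble controls on placebo.

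**The concern.** One power statement is made to serve two contrasts that have different sample sizes. Controls v CSA/MDD can use 23 v 23. Amisulpride v placebo within CSA/MDD has half that number.

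The effects behind the statement also mix two quantities: how far patients differ from controls, and how far a drug moves people. The drug values come from other agents. The pramipexole value also comes from a task that this trial runs in the ERP session, while amisulpride is given in the fMRI session. These two values are the largest in their sets, so they raise both averages.

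At stake is how precisely the trial can estimate the amisulpride effect in the group where the plan expects the largest gain. A reader of VI.d would reasonably take that contrast to be covered by the figure above 0.95.

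**Working it through.** **Inputs.** 23 per group (IV.a), split 1:1 (V, Randomization), so 11 v 12. Alpha 0.05 (VI.d), with sidedness not stated. Effects as listed in VI.d.

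**The plan's averages.** Behaviour: (0.85 + 0.70 + 1.45)/3 = 1.00. fMRI: (0.78 + 0.87 + 1.80)/3 = 1.15. Both reproduce, and each contains one drug effect.

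**The plan's power figure.** Two-sample t-test with noncentrality δ = d/√(1/n₁ + 1/n₂) and n₁ + n₂ − 2 degrees of freedom. At 23 v 23, √(2/23) = 0.295:

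- d = 1.00: δ = 3.39, power 0.955 one-sided, 0.912 two-sided.
- d = 1.15: δ = 3.90, power 0.986 one-sided, 0.968 two-sided.

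So the figure above 0.95 reproduces for both components at 23 v 23 if the test is one-sided. Two-sided, it reproduces for fMRI only.

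**The drug contrast within CSA/MDD.** √(1/11 + 1/12) = 0.417 and df = 21. The critical t is 2.080 two-sided and 1.721 one-sided.

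| d | Source | δ = d/0.417 | Two-sided | One-sided |
|---|---|---|---|---|
| 0.78 | MID deficit, maltreated sample | 1.87 | 0.43 | 0.57 |
| 0.85 | PSST deficit, women with CSA and MDD | 2.04 | 0.49 | 0.63 |
| 0.87 | MID deficit, unmedicated MDD | 2.08 | 0.51 | 0.65 |
| 1.00 | plan's behavioural average | 2.40 | 0.63 | 0.75 |
| 1.15 | plan's fMRI average | 2.76 | 0.75 | 0.85 |
| 1.45 | pramipexole | 3.47 | 0.91 | 0.96 |
| 1.80 | bupropion | 4.31 | 0.98 | 0.99 |

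The first three rows equate the drug effect with the placebo deficit. That is an inference from the normalisation prediction and assumes a common SD. The three regional values listed behind 0.87 (0.98, 0.73, 0.78) average 0.83. Power at 0.83 is 0.48 two-sided, inside the range.

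**Detectable effect at 11 v 12.** 80% power needs d = 1.23 two-sided or 1.07 one-sided. 95% power needs 1.58 or 1.42. A two-sided 95% confidence interval would have a half-width of about 2.080 × 0.417 = 0.87 SD.

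**Sensitivity.** With 5% loss (11 v 11), two-sided power is 0.41 to 0.49 for d = 0.78 to 0.87, and 0.61 and 0.73 at the two averages. With the error term pooled over all eight cells (84 df), it is 0.46 to 0.54 for d = 0.78 to 0.87, and 0.66 and 0.78 at the averages.

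**Pooled drug test, 46 v 46 (one trial type).** √(2/46) = 0.209 and df = 90. An average drug effect of 0.78 over the four groups gives δ = 3.74 and two-sided power 0.96. If the average is only half of 0.85 (0.425), δ = 2.04 and power is 0.52. The 80% detectable average effect is about 0.59.

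**The case against.** Several points on the other side are sound.

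- **The wording of the claim.** The figure above 0.95 is stated for differences between groups, not separately for the drug contrast. A reader might infer that the plan claims 0.95 for amisulpride v placebo in CSA/MDD; it does not say so. What stands is that a contrast named as a basis for the sample size has no power figure of its own, and the one figure given rests on averages that include drug effects.
- **The place of the contrast.** A reader might take it as the central test of Aim 1. Section VI.a lists no within-CSA/MDD drug test. It lists Drug x Trial Type, the three-way interaction, main effects, and comparisons with placebo controls. Hypothesis 1a predicts improvement on drug generally, and the pooled test addresses that better.
- **The implied effect.** The range 0.78 to 0.87 is inferred. The plan says no difference or similar activation, which is not a statement of equal means. Only the PSST value comes from women with both CSA and MDD. Section VI.a ranks CSA/MDD below MDD on activation, so its fMRI deficit could exceed 0.87. The result at 1.00 and 1.15 does not depend on this inference.
- **Overshoot.** A reader might infer that 1.45 or 1.80 would push CSA/MDD above placebo controls and so contradict the plan. That subtracts effects measured on different tasks, brain regions and samples, and the documents do not support it.
- **The interaction.** On one trial type at d = 0.85, with no gain elsewhere, Group x Drug has power of about 0.30 for CSA/MDD v controls (SE = √2 × 0.417, 84 df) and 0.41 for CSA/MDD v the other three groups (SE = √(4/3) × 0.417). A reader might turn the first into a minimum miss rate of 70%. It is not a bound: the planned test also uses trial type, and the documents give neither the correlation between trial types nor the size of the shift on punishment trials. These figures are illustrative only.

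**Conclusion.** The concern holds in a limited form. The design does not deliver power above 0.95 for the CSA/MDD drug contrast at the plan's averaged effects, one- or two-sided: 0.63 and 0.75 two-sided, 0.75 and 0.85 one-sided. If the drug effect equals the placebo deficit, two-sided power falls to about 0.43 to 0.51. Among the effects cited, 0.95 is reached only at the other-drug values: 1.45 if one-sided, and 1.80 either way.

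This rests on 11 v 12 analysed and a two-sample comparison at alpha 0.05. The lower range further assumes full normalisation, a common SD, and partly proxy samples. Two-sided is the fairer basis because the planned ANOVAs are non-directional.

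It does not follow that the drug question as a whole is underpowered; the pooled test may be adequate, depending on the average effect over the four groups. Nor do the documents say how a non-significant result would be interpreted, so no claim is made about that.

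**What to change.** In section VI.d:

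1. Stop averaging drug effects with case-control deficits. Label the pramipexole and bupropion values as context from other drugs.
2. Attach to every power figure the contrast, the n per arm and the sidedness it applies to.
3. State power for amisulpride v placebo in CSA/MDD at 11 to 12 per arm over d of about 0.78 to 1.15 (about 0.43 to 0.75 two-sided), with the 80% detectable d of about 1.23.
4. Give power for the pooled four-group drug test (46 v 46) already planned in VI.a, as the better-powered test of Hypothesis 1a, with the average effect it assumes.

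In section VI.a, commit to reporting the CSA/MDD drug effect and the Group x Drug interaction with confidence intervals.

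The cost is wording only, with no new subjects or data. The Randomization text says the blind was already broken for preliminary analyses and foresees only a few further participants, so the gain lies in honest reporting rather than a changed design. The downside is that the stated power for the drug contrast becomes much less favourable.
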